**4. Study Procedures**

- a. Study design, including the sequence and timing of study procedures (distinguish research procedures from those that are part of routine care).

**Design:** Prospective Randomized Clinical Trial – Pilot Study

**Sequence and timing:**

- A. Screening by Tracheostomy Nurse Practitioner following percutaneous tracheotomy
1. Glasgow Coma Scale (GCS)
  2. Richmond Agitation Sedation Scale (RASS)
- B. Speech-Language Pathologist consult is placed for patients meeting study inclusion criteria
- C. Patient consent is obtained by Tracheostomy Nurse Practitioner or Speech-Language Pathologist
- D. Randomization into Intervention and Control groups
- E. Session 1 within 12-24 hours following percutaneous tracheotomy:
1. Both groups complete pre-assessment consisting of the following:
    - i. Electronic Patient Records (POE, EPR, or EPIC)
      1. Demographic Data
      2. Patient Characteristics
      3. Sequential Organ Failure Assessment (SOFA)
    - ii. Confusion Assessment Method for the ICU (CAM-ICU)
    - iii. Health-related quality of life survey, Quality of Life – Mechanical Ventilation (QOL-MV)
    - iv. Tracheostomy-related assessment
      1. Trach size
      2. Mechanical ventilation status
      3. Secretions & tolerance of cuff deflation
      4. Presence of complications
        - i. Bleeding at stoma
        - ii. Subcutaneous air
        - iii. Infection at stomal site
        - iv. Pneumothorax
        - v. Accidental decannulation
  2. Intervention Group completes standard SLP evaluation and OWSV trial:
    - i. SLP evaluation includes the following to assess candidacy for OWSV trial:
      1. Level of alertness
      2. Cranial nerve exam
      3. Ability to cough
      4. Ability to tolerate cuff deflation
      5. Ability to tolerate finger occlusion
      6. Vocal quality
    - ii. If appropriate, OWSV will be trialed and assessed for the following:
      1. Duration of tolerance
      2. Change in vital signs
      3. Vocal quality
      4. Presence of air trapping
      5. Sentence Intelligibility Test
    - iii. Recommendations are made for OWSV use outside of SLP supervision
      1. Supervision requirement (RN, Respiratory therapist, trained family, independent)
      2. Duration of OWSV use
  3. Control Group receives no further evaluation or treatment during Session 1, which constitutes current standard of care.
- F. Session 2 within 48-60 hours following percutaneous tracheotomy:
1. Both groups complete post-assessment:

Date: 2/06/18

Principal Investigator: [name]

Application Number: IRB00080981

[figure not shown]
- i. Electronic Patient Records (POE, EPR, or EPIC)
    1. Demographic Data
    2. Patient Characteristics
    3. Sequential Organ Failure Assessment (SOFA)
  - ii. Health-related quality of life survey (QOL-MV)
  - iii. Confusion Assessment Method for the ICU (CAM-ICU)
  - iv. Tracheostomy-related assessment
    1. Trach size
    2. Mechanical ventilation status
    3. Secretions & tolerance of cuff deflation
    4. Presence of complications
      - i. Bleeding at stoma
      - ii. Subcutaneous air
      - iii. Infection at stomal site
      - iv. Pneumothorax
      - v. Accidental decannulation
  2. Intervention Group completes second SLP evaluation and OWSV trial.
  3. Control Group completes initial SLP evaluation and OWSV trial.
- G. Session 3 following first trach change
1. Both groups receive follow-up SLP re-evaluation and OWSV trials as appropriate per standard of care.

**Setting:** All ICUs at the Johns Hopkins Hospital

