#### **Specific Aim 3: Determine the effect of early use of the OWSV on clinical outcomes.**

Hypothesis 3a: The increase in the health-related quality of life scores from pre- to post- assessment will be significantly higher in the patients who receive early OWSV compared to those who receive it the traditional way 48 hours after undergoing a tracheostomy.

Hypothesis 3b: There will be no significant changes in the rate of complications between patients receiving early versus standard use of the OWSV.

Hypothesis 3c: Patients who begin to use the OWSV early will have a significantly shorter lengths of stay in the ICU than patients who start using OWSV after 48 hours.

**3. Background** (briefly describe pre-clinical and clinical data, current experience with procedures, drug or device, and any other relevant information to justify the research)

Current standard of care to wait 48 hours following tracheostomy procedure to initiate OWSV assessment and treatment, however, there is scant evidence in the literature justifying this amount of time. 201 patients out 272 patients who received a tracheostomy received SLP consult for in 2014. Based on prior data from the tracheostomy database 30% of mechanically ventilated and / or tracheotomized patients tend to be awake and interactive, and attempt to communicate.

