**Study Protocol**

Date: 2/06/18

Principal Investigator: [name]

Application Number: **IRB00080981**

- b. Study duration and number of study visits required of research participants.

The study duration is estimated to be 4 weeks per patient with a total of 3 visits by the study team.

- c. Blinding, including justification for blinding or not blinding the trial, if applicable.

Patients will not be blinded to intervention or control group.

- d. Justification of why participants will not receive routine care or will have current therapy stopped.

If patient is not willing to participate in the study, their routine care will not be altered. Participants in the control group will receive routine care, and participants in the intervention group will initiate the same intervention as routine care with timing to be 24-60 hours earlier than the current routine care.

- e. Justification for inclusion of a placebo or non-treatment group.

N/A

- f. Definition of treatment failure or participant removal criteria.

If there is a change in clinical condition that prevents study team from continuing with OWSV trial or if the patient is discharged from the hospital, the patient will be removed from the study.

- g. Description of what happens to participants receiving therapy when study ends or if a participant's participation in the study ends prematurely.

If participants receiving the OWSV complete the study (after Session 3), they will continue to use the OWSV per our current standard of care. If the participant's participation using the OWSV ends prematurely due to change in clinical condition, then they will be dropped from the study. But if their condition improves and warrants reuse of the OWSV, they will be offered the OWSV per our standards of care but will not be re-enrolled in the study.

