## 8. Risks

- a. Medical risks, listing all procedures, their major and minor risks and expected frequency.  
Risks of OWSV use include development of subcutaneous air and air trapping that could lead to respiratory distress.

Administration of questionnaires repeatedly can be burdensome. In addition, questions about their quality of life while mechanically ventilated may be emotionally distressing.

- b. Steps taken to minimize the risks.

Patients will be screened by the tracheostomy nurse practitioner for inclusion in the study, and all patients enrolled in the study will undergo thorough evaluation with an SLP per standard protocol, prior to the trial with the OWSV. Trial of the OWSV will be deferred if the SLP determines that the patient is not an appropriate candidate to trial the OWSV at the time. The SLP will follow standard protocol during OWSV trials of appropriate candidates. OWSV trials will be discontinued and SLP will refer to the medical team if the patient experiences any complications.

During administration of questionnaires, the interviewer will stop the interview and refer to the medical team providing care in the ICU if at any time the participant appears upset or distressed. The interviewer will remain with the participant until she or he has regained emotional equilibrium. If the participant states that he/she is tired and would like to rest, the interviewer will stop the interview and come back at a later time to continue with the interview. The participant may wish to withdraw from the study anytime they choose to.

- c. Plan for reporting unanticipated problems or study deviations.

The PI will discuss any unanticipated problems of study deviations that pertain to the participants' health with the medical team caring for the patient.

Date: 2/06/18

Principal Investigator: [name]

Application Number: **IRB00080981**

- d. Legal risks such as the risks that would be associated with breach of confidentiality.  
Data will be stored in RedCap database that is password protected on the ICTR server. The database can only be accessed by the study team and the PI. Upon, completion of data collection, names and medical record numbers will be removed. A new research ID number will be assigned for analysis. Any document that may re-identify the patient will be destroyed. Once the data are de-identified, then analysis will begin.
- e. Financial risks to the participants.  
N/A

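### Randomisation is listed before the pre-assessment and nothing withholds the arm, so the baseline QOL-MV for Hypothesis 3a may be recorded with allocation known; this is cheap to avoid

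*Combined protocol and SAP*

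**What the plan says.** Section 4a (Sequence and timing) gives a lettered order: screening (A), SLP consult (B), consent (C), then step D, "Randomization into Intervention and Control groups". Step E follows: "Session 1 within 12-24 hours following percutaneous tracheotomy". Its first item, E.1, reads "Both groups complete pre-assessment consisting of the following", and the QOL-MV is item E.1.iii.

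The arms part company only after that. E.2 gives the intervention group the SLP evaluation and valve trial. E.3 says "Control Group receives no further evaluation or treatment during Session 1". The QOL-MV is given again to both groups in the Session 2 post-assessment.

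Hypothesis 3a (Specific Aim 3) uses the two scores as a change: "The increase in the health-related quality of life scores from pre- to post- assessment will be significantly higher" in the early group.

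On masking, section 4c says "Patients will not be blinded to intervention or control group" and says nothing about the person collecting the data. Section 8b shows that the questionnaires are given by interview: "During administration of questionnaires, the interviewer will stop the interview and refer to the medical team" if the participant becomes distressed.

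**The concern.** A baseline score should not be open to influence from the allocation. As the steps are listed, the groups already exist when the QOL-MV is first given, the patient is not blinded, and the interviewer is not said to be unaware of the arm. A patient who knows that a speaking valve will be tried that session, or that it will not be offered until Session 2, may answer quality-of-life questions differently. An interviewer who knows the arm may also influence the answers.

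Hypothesis 3a subtracts this score from the Session 2 score, so an arm-related shift in it passes straight into the comparison. It would also weaken the score as a baseline descriptor or adjustment variable. The design does not need this order, because nothing differs between the arms until E.2 and E.3.

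**Working it through.** **Order and masking, side by side**

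| Question | Where | What the plan gives |
|---|---|---|
| When is the arm assigned? | 4a, step D | After consent, before Session 1 |
| When is the baseline QOL-MV taken? | 4a, E.1.iii | Session 1, in groups already formed |
| Is the patient blinded? | 4c | No |
| Is the interviewer unaware of the arm? | 4c, 8b | Not stated |
| When is the arm disclosed? | No section | Not stated |
| Where do the arms diverge? | 4a, E.2 and E.3 | After E.1 |
| Is the primary outcome measured at E.1? | 4a, 7a | No; the intelligibility test is not in the E.1 list |

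The exposure is therefore possible under the stated order, but not established. It concerns one secondary outcome.

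**Would the data reveal a shift?** Section 7c plans 25 per arm. In SD units of the score:

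- SE of the between-arm baseline difference = sqrt(2/25) = 0.283 SD.
- 95% half-width = 2.011 × 0.283 = 0.569 SD (48 degrees of freedom).
- A two-sided 5% t-test would flag an assumed shift of 0.1, 0.3 or 0.5 SD with probability 0.06, 0.18 or 0.41.

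These figures follow from the sample size alone. They show that a baseline comparison would be a poor safeguard, not that a shift occurs.

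**Does an earlier baseline reduce the net bias?** Suppose that knowing the arm shifts the QOL-MV by d between arms, and that a share p of the shift is still present at Session 2. Both are assumptions.

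- Listed order, arm known at E.1: bias in the difference in change = p·d − d = −(1 − p)d.
- Baseline before disclosure: bias = p·d − 0 = p·d.

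With d = 0.3 SD for illustration:

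| p | Listed order | Baseline before disclosure |
|---|---|---|
| 0 | −0.30 | 0 |
| 0.5 | −0.15 | +0.15 |
| 1 | 0 | +0.30 |

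The two are equal in size at p = 0.5. The earlier baseline gives the smaller change-score bias only if less than half of the shift persists. If the analysis instead adjusts for baseline, with an assumed pre-post correlation of 0.5 and equal SDs, the biases are (p − 0.5)d and p·d. The earlier baseline then gives the smaller bias only if p is below 0.25. The documents say nothing about d or p.

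Section 7c names only paired t-tests of pre and post scores and no between-arm test for Hypothesis 3a. No error rate of a planned test can therefore be attached to these biases.

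**Numbers available.** The plan's own figure reproduces: 55 × (1 − 0.10) = 49.5, rounded to 50. There is no slack if patients are lost between consent and randomisation. An assumed loss of 2%, 5% or 10% leaves 49.5 × 0.98 = 48.5, 49.5 × 0.95 = 47.0 or 49.5 × 0.90 = 44.6. The difference detectable with 80% power (two-sample t-test, two-sided 5%, illustrative) moves from 0.81 SD at 50 to 0.82, 0.84 or 0.86 SD.

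**The case against.** The strongest objection is that the algebra above does not favour the change. Patients remain unblinded at Session 2, so a shift could well persist. If it persists fully, the listed order cancels it and the earlier baseline leaves +0.30 SD in the example. If knowing one is in the early arm raises scores, the listed order works against Hypothesis 3a and the change works towards it. This stands as far as it goes: a smaller net bias cannot be promised. But the cancellation would be accidental. The Session 2 open-label effect is present under either order, and the listed order adds a second error of unknown size in the baseline.

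The exposure is also inferred. Unblinded does not mean told before E.1, and step D does not say when the arm is revealed. This is correct, and if disclosure in practice falls at E.2, one sentence saying so settles the point. A reader might infer that patients know their arm for nearly 24 hours before baseline. That would need steps A to D to finish almost at once after the procedure and E.1 to fall at the end of its window, and the documents give no such interval.

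The scope is narrow: one secondary outcome in a 50-patient pilot. The lack of a named between-arm test and the unblinded Session 2 score may each limit Hypothesis 3a more. This bears on priority, not on whether to make a near-free change.

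A reader might also infer that patients are randomised before eligibility is settled, because section 5 requires a negative CAM-ICU and section 4a first lists it at E.1.ii. The documents do not support that. Step B already applies to patients who meet the inclusion criteria, and since CAM-ICU is repeated at Session 2, E.1.ii can be read as the first of two study measurements. Listing it under step A would be a clarification only.

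**Conclusion.** The point holds as a cheap improvement. Under the stated order the baseline QOL-MV for Hypothesis 3a may be recorded with the arm known, and nothing in the plan prevents this. It rests on the listed sequence, on patients being unblinded, on interviewer administration, and on silence about disclosure; interviewer awareness is unstated, not declared.

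The size and direction of any bias cannot be derived from the documents, and the SD figures above are illustrations under assumed shifts. The documents do not support reading this as an inflated false-positive rate, a loss of power, or a demonstrated bias in Hypothesis 3a. Nor does the point reach the primary outcome. What the change secures is a baseline free of allocation, so that any effect of knowing the arm can enter only through the Session 2 score.

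**What to change.** Choose one of two options:

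1. After consent, complete E.1 in all patients within the same 12-24 hour window, then randomise and reveal the arm immediately before E.2.
2. Keep randomisation at step D, but state that the arm is withheld from the patient and from the QOL-MV interviewer until E.1 is recorded.

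In either case, state the disclosure point in section 4c, and acknowledge there or with Hypothesis 3a that the Session 2 QOL-MV remains unblinded.

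Cost: no new procedures and no change of window. Under both options Session 1 SLP time must be arranged before the arm is known, so up to 25 of 50 slots (the control half) would not be used for an evaluation. Step B already places an SLP consult for each eligible patient, which limits this. Option 1 may lose a few patients before randomisation, with the small effect on precision shown above or a somewhat longer recruitment period. Option 2 leaves the number randomised unchanged.

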#### **Specific Aim 2: Determine the effect of the early use of the OWSV on the quality of speech.**

Hypothesis 2a: The increase in the speech intelligibility scores from pre- to post- assessment will be significantly higher in the patients who receive early OWSV compared to those who receive it the traditional way 48 hours after undergoing a tracheostomy.

Research Question 2b: Is the duration of speech longer for patients who start using OWSV earlier compared to those who start late?

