**Instruments:**

Name	Concept measured	Number of items
QOL-MV	Quality of life in mechanically ventilated patients questionnaire	12
SIT	Sentence intelligibility test	11
SOFA	Sequential Organ Failure Assessment Tool	6
Additional questions	Demographic Data	

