## 7. Study Statistics

- a. Primary outcome variable.

Speech intelligibility

- b. Secondary outcome variables.

- Patient characteristics
- Quality of Life
- Complications
- Time to events
- Length of stay
- Mortality

\*See codebook for list of additional variables

- c. Statistical plan including sample size justification and interim data analysis.

Mean, standard deviation, median and inter-quartile range will be calculated for continuous variables. Paired t-tests will be used to compare pre and post assessment scores for continuous variables. Frequencies and percentages will be calculated for categorical variables. Chi square and Fisher Exact tests will be used to compare pre and post assessment scores of categorical variables. Sample size is estimated based on 30% of tracheostomy patients who might be awake and interactive at the Johns Hopkins Hospital in 2016, as per the tracheostomy database. According to the 2014 data, we found that about 55 patients were awake and interactive while having a percutaneous tracheostomy tube at the hospital. Considering a 10% of the patients who may not be interested in the study, we will plan for a sample size of 50 with 25 in the intervention group and 25 in the control group.

- d. Early stopping rules.

If patients have changes in clinical condition that prevents cuff deflation, they will be dropped from the study. The study will be halted if any major complications occur from early trial of OWSV.

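### The primary outcome test is scheduled once, inside a conditional Session 1 valve trial in one arm, so Session 2 scores are either unscheduled or limited to patients judged valve candidates after randomisation

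*Combined protocol and SAP*

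**What the plan says.** Section 7a gives the primary outcome as "Speech intelligibility". The Instruments table lists one matching tool, "Sentence intelligibility test", with 11 items and no visit or group. Hypothesis 2a is a between-arm statement: "The increase in the speech intelligibility scores from pre- to post- assessment will be significantly higher in the patients who receive early OWSV" than in those treated at the usual time.

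In section 4a, Sequence and timing, randomisation is step D. The schedule then runs as follows.

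- **Session 1, intervention arm (E.2).** The speech-language pathologist (SLP) first assesses candidacy, including finger occlusion and vocal quality. Then comes "If appropriate, OWSV will be trialed and assessed for the following", and item 5 of that list is "Sentence Intelligibility Test". The schedule names the test nowhere else.
- **Session 1, control arm (E.3).** No SLP evaluation and no valve trial.
- **Session 2, both arms (F.1).** Records and SOFA, QOL-MV, CAM-ICU and the tracheostomy assessment. The SIT is not listed.
- **Session 2, by arm (F.2, F.3).** "Intervention Group completes second SLP evaluation and OWSV trial"; "Control Group completes initial SLP evaluation and OWSV trial". Neither line names the SIT or repeats the Session 1 condition.

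Section 8b, which covers all enrolled patients, says "Trial of the OWSV will be deferred if the SLP determines that the patient is not an appropriate candidate". Section 4f removes patients whose condition stops the valve trial from continuing and those discharged. Section 7d drops those in whom cuff deflation becomes impossible. Section 7c has no rule for patients without a SIT and names no analysis set.

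**The concern.** A secondary outcome, QOL-MV, is scheduled for everyone at both sessions, while the primary outcome is tied to a procedure that not every patient will undergo. Whether a patient undergoes it at Session 2 depends on a judgement made after randomisation, and early valve use could affect that judgement. By then the intervention arm has had an earlier evaluation and possibly valve practice; the control arm has had neither. Patients are not blinded (section 4c), and blinding of the SLP is not stated.

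A comparison restricted to scored patients is then no longer a comparison of the groups that were randomised. If early use turns marginal patients into candidates, their scores enter one arm only. If early use sets some patients back, they leave that arm's mean. The first can make early use look worse than it is, and the second better. With 25 patients per arm planned, each missing score also costs precision.

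**Working it through.** **1. What the schedule yields at Session 2.** There are two readings.

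- *Literal:* the SIT is in none of F.1, F.2 or F.3, so neither arm has a scheduled Session 2 score.
- *Carry-over:* the valve trial in F.2 and F.3 has the Session 1 content, so the SIT is included. The Session 1 condition then comes with it, and section 8b applies that condition to every enrolled patient. Only candidates are scored, and sections 4f and 7d remove further patients for related reasons.

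Neither reading gives a Session 2 score, or a recorded status in its place, for each randomised patient.

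**2. The plan's own figure.** Section 7c starts from about 55 available patients and allows 10% for refusal: 55 × 0.90 = 49.5, rounded to 50, or 25 per arm. This reproduces. It is a feasibility count: the plan gives no alpha, power, effect size or SD, and no allowance for patients without a score.

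**3. Precision.** Assume a two-sided 0.05 test, 80% power and a normal approximation. The detectable difference in SD units is (1.960 + 0.842) × √(2/n). The scored shares are assumptions. Power is for the 0.79 SD difference that 25 per arm would detect.

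| Share scored | n per arm | Detectable difference | Power at 0.79 SD |
|---|---|---|---|
| 100% | 25 | 0.79 SD | 80% |
| 80% | 20 | 0.89 SD | 71% |
| 70% | about 18 | 0.93 SD | 66% |
| 60% | 15 | 1.02 SD | 58% |
| 50% | about 12 | 1.14 SD | 49% |

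**4. Bias when there is no true effect.** Suppose fitness for the valve and intelligibility are correlated normal variables with correlation ρ, and a share p of each arm is judged fit. The mean score among the fit is shifted by ρ × φ(z)/p, where z is the normal cut-off leaving a share p above it. For p = 0.60, φ(z)/p = 0.644; for p = 0.80 it is 0.350. The spurious difference is therefore ρ × 0.294, in favour of the arm with fewer fit patients.

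| Fit shares | ρ | Spurious difference | Actual type I error |
|---|---|---|---|
| 70% and 70% | any of those below | 0 | 5% |
| 60% and 80% | 0.3 | 0.09 SD | 5.8% |
| 60% and 80% | 0.5 | 0.15 SD | 7.5% |
| 60% and 80% | 0.7 | 0.21 SD | 10.7% |
| 50% and 80% | 0.3 | 0.13 SD | 6.7% |
| 50% and 80% | 0.5 | 0.22 SD | 10.3% |
| 50% and 80% | 0.7 | 0.31 SD | 17.5% |

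All shares and correlations are assumed. Equal shares give no bias in this model.

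**5. How the choice of patients can matter.** Assume 60% are candidates in either arm (mean SIT 85), 20% become candidates only with early use (mean 60), and 20% never do.

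- Scored patients only: early (0.6 × 85 + 0.2 × 60)/0.8 = 63/0.8 = 78.75; control 51/0.6 = 85; difference −6.25.
- All randomised, no valve-assisted speech counted as 0: early 51 + 12 = 63; control 51; difference +12.

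The two analyses answer different questions, and this scenario was chosen to separate them. It shows that they can disagree in sign, not that they will here.

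**The case against.** Four points can be made for the plan.

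- **F.2 and F.3 say that each group completes an evaluation and valve trial, without the Session 1 condition.** This stands as a limit: the Session 2 condition is inferred from section 8b and is not written into those lines. It does not rescue the schedule. If the Session 1 content does not carry over, no SIT is scheduled; if it does, the condition carries over too.
- **The codebook cited in section 7b may define a SIT variable.** It is not among the documents and cannot be checked. A variable list alone would not say how deferred patients are handled.
- **Eligibility already selects likely candidates:** GCS of at least 9, CAM-ICU negative, RASS −1 to +1, no known severe airway obstruction and no foam-filled cuff. This may narrow the share of non-candidates. It does not remove it, since candidacy is still assessed after enrolment.
- **This is a pilot sized on feasibility, and tolerance already belongs to Aim 1.** It is fair to say that merging tolerance with clarity of speech is a choice. Reporting candidacy and SIT among users side by side is defensible, but the plan states neither that nor any rule for untested patients.

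A reader might also infer that a deferred patient is known to have no intelligible speech. The documents do not support that. Section 8b defers the trial for the time being, and finger occlusion and vocal quality are assessed before any valve is placed. A deferral shows only that no valve-assisted test took place then.

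**Conclusion.** The point holds on the text: the Session 2 measurement of the primary outcome is either unscheduled or conditional on a judgement made after randomisation, and the plan has no rule for patients without a score. Supplying the missing control baseline would not cure this, because it concerns who has a post score.

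That the scored groups can differ by arm follows from the design. That they will differ, by how much and in which direction, is unknown, because the documents give no candidacy rates. A reader might take the change from −6.25 to +12 as evidence that the planned comparison would mislead against early use. It rests wholly on assumed shares and means, and harm from early use would push the other way. The spurious differences of 0.09 to 0.31 SD likewise hold only for unequal fit shares and the assumed correlations.

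**What to change.** 1. List the SIT in F.1 as a Session 2 post-assessment for both arms. Where the SLP defers the valve, that clinical decision stays as it is; the form records that the patient was not tested, and why.
2. Reconcile sections 4f and 7d with this, so that patients who cannot continue the valve trial stay in the analysis set with their status recorded. Otherwise the added line in F.1 would not reach them.
3. Report by arm, among all randomised patients, the proportion able to complete a valve-assisted SIT.
4. Include an all-randomised rank comparison of the Session 2 score in which patients untested because of candidacy rank lowest, defined as having no valve-assisted intelligible speech. Ranks remove dependence on the floor's numerical value, but not the assumption that these patients belong below every tested one. State separately how scores missing for other reasons, such as discharge, are handled.
5. Label SIT among valve users as descriptive.
6. State that this compares Session 2 scores and not the pre-to-post increase of Hypothesis 2a, since controls have no Session 1 SIT.

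The cost is one schedule line, one form field for the reason, edits to 4f and 7d, and a short analysis paragraph. No visit is added. The downside is that the ranked score mixes ability to use the valve with clarity of speech, so both components must be shown separately.

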### 2. Objectives (include all primary and secondary objectives)

#### **Specific Aim 1: Identify patients who would benefit from early use of the OWSV.**

Hypothesis 1a: Several factors such as age, sex, educational level, primary diagnosis, indication for tracheostomy, co-morbidities, and severity of illness will significantly contribute to early tolerance of the OWSV.

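### Tolerance time is right-censored for patients whose supervised valve trial ends while they still tolerate the valve, but the plan summarises it as a complete value

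*Combined protocol and SAP*

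**What the plan says.** Section 4a (Sequence and timing, item E.2.ii) introduces the valve trial in the intervention group at Session 1 with "If appropriate, OWSV will be trialed and assessed for the following". The first item in that list is "Duration of tolerance". No unit, maximum length, definition of the end of tolerance, or code for a patient who is still tolerating is given.

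Item E.2.iii follows directly: "Recommendations are made for OWSV use outside of SLP supervision". It covers the level of supervision, up to independent use, and a recommended duration of use.

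Section 8b says when a trial is stopped for cause: "OWSV trials will be discontinued and SLP will refer to the medical team if the patient experiences any complications". Section 4f removes a patient whose clinical condition changes so that the trial cannot continue. Neither rule covers a trial that is going well.

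At Session 1, "Control Group receives no further evaluation or treatment during Session 1". At Session 2, "Control Group completes initial SLP evaluation and OWSV trial", and the intervention group has its second trial.

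Hypothesis 1a (section 2) makes tolerance the dependent variable. It lists factors from age to illness severity and ends "severity of illness will significantly contribute to early tolerance of the OWSV". It does not say whether tolerance is a duration or a yes/no result.

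Section 7c states: "Mean, standard deviation, median and inter-quartile range will be calculated for continuous variables". It adds paired t-tests of pre- against post-assessment scores. Section 7b lists time to events as a secondary outcome without naming the events, and refers to a codebook that is not part of the documents.

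**The concern.** A time measured inside a supervised session has two possible endings. Either the patient stops tolerating the valve, and the tolerance time is known, or the session stops first, and only a minimum is known. The step to use outside SLP supervision shows that the plan expects the second ending, and expects it in the patients who do best. Averaging both kinds of value as if they were complete pulls the mean down, most strongly in the groups with the longest tolerance.

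What is at stake is Hypothesis 1a, the only hypothesis under Specific Aim 1. The duration is the one item in the valve-trial list that carries the name tolerance. If it is used as the outcome, a characteristic that predicts long tolerance will show a weaker association than it really has. If the record does not show how each trial ended, the two kinds of value cannot be separated afterwards.

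**Working it through.** **The plan's own figure.** The only related figure is the sample size in section 7c: 55 × (1 − 0.10) = 49.5, rounded to 50, or 25 per arm. It reproduces. The point made here does not change it. The documents give no tolerance time, trial length or variance, so the size of the effect cannot be derived from them.

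**Illustration. All inputs in this part are assumptions.** Tolerance times are exponential. Two patient groups have true medians of 60 and 30 minutes. Every trial that has not already failed is ended at c minutes.

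1. True mean m = median / ln 2. This gives 60 / 0.693 = 86.56 and 30 / 0.693 = 43.28, a difference of 43.28 minutes.
2. True standardised difference. For an exponential the SD equals the mean, so the pooled SD is √[(86.56² + 43.28²)/2] = 68.4, and 43.28 / 68.4 = 0.63.
3. Share still tolerating at c: S = 2^(−c/median). At c = 30 this is 2^(−0.5) = 0.71 and 2^(−1) = 0.50.
4. Recorded mean: m(1 − S). At c = 30 this is 86.56 × 0.293 = 25.35 and 43.28 × 0.50 = 21.64, a difference of 3.71 minutes.
5. Recorded SD, from E[T²] = 2m²[1 − S(1 + c/m)] minus the squared mean. At c = 30 the SDs are 8.60 and 10.32, the pooled SD is 9.50, and 3.71 / 9.50 = 0.39.

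The same formulas at other assumed ending times give:

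| Trial ended at | Still tolerating (60 / 30 group) | Recorded means | Difference (true 43.3) | Standardised difference (true 0.63) |
|---|---|---|---|---|
| 15 min | 84% / 71% | 13.8 / 12.7 | 1.1 | 0.29 |
| 30 min | 71% / 50% | 25.4 / 21.6 | 3.7 | 0.39 |
| 60 min | 50% / 25% | 43.3 / 32.5 | 10.8 | 0.51 |

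The loss on the standardised scale is smaller than the minutes suggest, because ending trials early shrinks the spread as well as the difference.

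**The median.** Section 7c also plans medians. A median is undistorted while fewer than half of the patients are still tolerating at the end, and equals the ending time once more than half are. At 30 minutes, the group with a true median of 60 is recorded with a median of 30.

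**Events available to Hypothesis 1a.** Only the intervention group has a valve trial at Session 1. If all 25 are trialled and 71% are still tolerating at the end, 25 × 0.29 gives about 7 observed failures. At 50% the figure is about 12. Hypothesis 1a names seven factors.

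**The case against.** The case for leaving the plan alone has several sound parts.

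- No visit length or maximum trial time is stated. A reader might infer that good tolerators' values are simply fixed by how long the SLP stays. The documents do not say what ends a successful trial or how many end that way. They support only that some trials end without failure.
- A reader might also infer that a between-arm t-test would mistake unequal visit lengths for a difference in tolerance. The documents do not support this. No between-arm t-test is planned, and nothing says that trial length differs by arm. The planned t-test is paired. Controls have no Session 1 trial, so it could be run on this variable only within the intervention group. Nor is tolerance time in the listed pre- and post-assessment.
- The duration is not a named outcome. It reaches section 7c only through the general sentence on continuous variables, and Hypothesis 1a could be read as yes/no.
- The unseen codebook may hold a field for why a trial ended. Air trapping and vital-sign changes are recorded in each trial and partly identify intolerance.
- Real predictors would be weakened but not hidden. For medians of 60 and 30 minutes, trials ended at 30 minutes and a hypothetical 25 per group, detection by a two-sample t-test falls from about 62% to about 28%.

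These points limit the concern without removing it. However the hypothesis is read, the plan offers no method for a time that may be a lower bound. Listing time to events does not supply one, since neither the events nor an analysis is defined.

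**Conclusion.** The concern holds in a limited form. Some recorded tolerance times will be right-censored, section 7c would treat them as complete, and the available documents show no item that separates a failed trial from one stopped while tolerated. If the duration is the outcome of Hypothesis 1a, means are understated and associations weakened. The amount is unknown. In the illustration the standardised difference falls from 0.63 to between 0.29 and 0.51, and those figures rest wholly on the assumed exponential times, medians and ending times.

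Speech intelligibility, the primary outcome, is unaffected. In a pilot of 50 patients this is a minor point. It is worth correcting because the reason a trial ended is easy to record at the time and hard to recover later.

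**What to change.** 1. Add one field to each valve trial for why it ended: intolerance or complication, or stopped while still tolerated. If the codebook already holds it, cite it in the protocol.
2. In section 7c, summarise tolerance time by Kaplan-Meier, with trials stopped while tolerated counted as censored, in place of the mean and t-test for this variable.
3. For Hypothesis 1a, state the outcome. Either use a yes/no result for still tolerating at one observation time common to all trials, chosen by the study team, or compare censored times for one factor at a time. Failures will be too few for a model with all seven factors.
4. Do not use the recommended duration of valve use (item E.2.iii) as a measure of tolerance. The SLP sets it; it is not a patient response.

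The cost is one case-report field and a few sentences in section 7c. The sample size and patient care do not change. The downsides are wider intervals and few events. The censored analysis also assumes that the SLP's decision to stop is unrelated to impending intolerance. Stopping because a patient is tiring would break that assumption, so the recorded reason should make such cases visible.
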